#### 5.4.2 Analyses of Secondary Outcomes

**Aims 2–4:** Similar analyses to that described for the primary analysis will be performed on the Clinical Dementia Rating Scale – Sum of Boxes (CDR-SB), ADAS-Cog13 total score, Executive Function and Episodic Memory Composites, tests of daily living skills (ADCS–Activities Of Daily Living–MCI [ADCS-ADL-MCI], Behavior Rating Inventory Of Executive Function–Adult Version [BRIEF-A]), mood and health-related quality of life (Neuropsychiatric Inventory [NPI], 36-Item Short-Form Health Survey [SF-36]), EuroQol 5-Item Health Questionnaire [EQ5D]), and subjective memory concerns (Cognitive Change Index).

**Aim 5:** Change in brain volume and inter-regional correlations in brain functional activity will be compared between treatment groups. The analysis will be completed separately for each volumetric and functional MRI parameter.

**Aim 6:** CSF biomarkers of brain health and disease will be examined using a similar analytic strategy to that described for the analysis of the primary outcome using MMRM and other sensitivity models to test for intervention effects. Covariate adjustment, sensitivity analyses, and multiple imputation analyses will be carried out as specified under Aim 1.

**Aim 7:** To examine whether sociodemographic factors, genotype, actigraphy outcomes, or baseline cognitive and biomarker profiles predict treatment response, MMRM and sensitivity models as described above will be performed using subgroup analyses. Model fitting and covariate adjustment will be carried out as specified under Aim 1.

**Aim 8:** To examine the enduring cognitive and behavioral effects of the intervention following the 6-month unsupervised exercise extension, MMRM and sensitivity models as described above will be performed. Model fitting and covariate adjustment will be carried out as specified under Aim 1.

**Aim 9:** To examine the impacts of the intervention on the study partner, MMRM and sensitivity models as described above will be performed on data obtained using the Study Partner Self-Assessment Questionnaire.

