## 1.2 Secondary Aims

**Aim 2:** To test the hypothesis that 12 months of aerobic exercise, relative to the control, will reduce clinical ratings of cognitive impairment as measured by the Clinical Dementia Rating Scale – Sum of Boxes, and total score on the ADAS-Cog13.

**Aim 3:** To test the hypothesis that 12 months of aerobic exercise, relative to the control, will improve executive function and episodic memory, as measured by domain-specific composite scores derived from ADAS-Cog-Exec subtests and other computer-administered tests (Cogstate, NIH Toolbox).

**Aim 4:** To test the hypothesis that 12 months of aerobic exercise, relative to the control, will improve daily living skills (ADCS–Activities Of Daily Living–MCI, Behavior Rating Inventory Of Executive Function–Adult Version), mood and health-related quality of life (Neuropsychiatric Inventory, 36-Item Short Form Health Survey, EuroQol 5-Item Health Questionnaire), and subjective memory concerns (Cognitive Change Index).

**Aim 5:** To test the hypothesis that 12 months of aerobic exercise, relative to the control, reduces the rate of regional and whole brain atrophy, and increases regional and whole brain perfusion assessed using volumetric and functional magnetic resonance imaging (fMRI).

**Aim 6:** To test the hypothesis that 12 months of aerobic exercise, relative to the control, will favorably alter AD biomarkers in CSF including beta-amyloid and tau, and to conduct exploratory analyses of exercise effects on other markers of brain health and disease in CSF and blood (e.g., brain-derived neurotrophic factor, vascular endothelial growth factor, measures of inflammation, proteomics/metabolomics).

**Aim 7:** To examine whether gender, age, baseline AD biomarker profile, apolipoprotein epsilon 4 (ApoE4) genotypes, total activity, and sleep integrity predict treatment response.

**Aim 8:** To examine the enduring cognitive and behavioral effects of the intervention following a 6-month extension, during which the assigned exercise is continued without supervision, to test a model for a community-based exercise prescription in adults with MCI.

**Aim 9:** To assess the impact of the intervention on the study partner's health, wellbeing and quality of life using the Study Partner Self-Assessment Questionnaire.

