### 5.4 Efficacy Analysis

#### 5.4.1 Analysis of Primary Outcome

To address **Aim 1** for the primary efficacy analysis, longitudinal scores from baseline through the first 12 months will be analyzed using a mixed effects model for repeated measures (MMRM) to assess differences in scores between intervention groups. The MMRM model will include terms for time, intervention, and baseline ADAS-Cog-Exec, intervention-by-time

interaction, baseline ADAS-Cog-Exec by time interaction, plus covariates that include site, ApoE4 carrier status, sex, and additional covariates meeting the criteria below.

Time will be treated as categorical. An analysis of covariance model imputing missing data with multiple imputation will be used as a sensitivity analysis. As a second sensitivity analysis, a similar MMRM model will be fit with time modeled as a continuous factor. If the longitudinal patterns over time are markedly non-linear, such as might occur due to learning effects, a quadratic term for time will be included in the model. In this case the intervention-by-time linear term assesses whether there is a relative difference between intervention groups that grows linearly with time. Potential confounders (baseline Walk Test time, age, education, 3MSE baseline score, and use of cholinesterase inhibitors) will be included in efficacy analyses as covariates if the following two conditions are satisfied: (1) imbalance at baseline ( $p < 0.1$ ) and, (2) association between the covariate and the response ( $p < 0.15$ ). Safety data will be analyzed using exact contingency table methods by intervention group assignment.

Differences in the primary outcome of change in ADAS-Cog-Exec between intervention groups will be tested at the two-sided 5% significance level. No adjustment to the type 1 error level will be made for secondary analyses.

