5.3 Exploratory Aims

- 5.3.1** To examine intervention effects on secondary outcomes listed above (**Section 5.2.2-5.2.4**) in participants who had the opportunity to complete a full 12 months of the study before the pandemic affected trial conduct.
- 5.3.2** To test whether 12 months of aerobic exercise, relative to the control, favorably affects MRI whole brain, ventricular and entorhinal volumes; perfusion in whole brain, gray matter and white matter; and individual AD biomarkers in CSF (ab42, ab40, total tau, p-tau, BDNF) and blood (ab42, ab40).
- 5.3.3** To test whether 12 months of aerobic exercise, relative to the control, reduces clinical ratings of cognitive impairment as measured by the CDR – Sum of Boxes, and total score on the ADAS-Cog13.
- 5.3.4** To test whether 12 months of aerobic exercise, relative to the control, improves self-report measures of cognitive function and well-being, including (1) daily living skills (ADCS–Activities of Daily Living–MCI); (2) BRIEF-A: Behavior Rating Inventory of Executive Function–Adult Version); (3) mood (GDS); (4) health-related quality of life (NPI: Neuropsychiatric Inventory; SF-36: 36-Item Short Form Health Survey; EuroQol: 5-Item Health Questionnaire); (5) subjective memory concerns (CCI: Cognitive Change Index); and (6) Study Partner Self-Assessment Questionnaire.
- 5.3.5** To examine enduring cognitive effects (measured by ADAS-Cog-Exec, Executive Function and Episodic Memory Composites) of the intervention following a 6-month extension (through Month 18) when the prescribed

exercise is continued without supervision.

- 5.3.6** To explore whether sex, age, baseline AD biomarker profile in CSF (ab42/ab40, ab42/tau, ab42/p-tau) and blood (ab42/ab40), and ApoE4 genotype (e4+, e4-) predict treatment response.

6. Populations of Interest

6.1 Modified Intent-to-Treat (mITT) Population: Includes all eligible participants who (1) began the exercise intervention (Intervention Session 1) and (2) completed at least one post-baseline assessment for the primary analysis at Month 6 or Month 12. All consented randomized participants are grouped according to the treatment assigned at randomization, regardless of any protocol violations.

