11.1 Analysis of the Primary Outcome

To address the aim for the primary analysis (**Aim 1**), longitudinal scores from baseline through Month 12 will be analyzed using a mixed effects model for repeated measures (MMRM) to test differences in ADAS-Cog-Exec (composite) change scores between intervention groups in the mITT Population, with type I error level set at 0.05.

The MMRM model includes terms for time, intervention assignment, and baseline ADAS-Cog-Exec plus covariates that include site, ApoE4 carrier status, sex, and additional covariates meeting the criteria below. The primary test compares group changes from baseline to the mean score obtained across the Month 6 and Month 12 assessments. When Month 6 or Month 12 data are missing for a participant, the endpoint consists of the score obtained at the available assessment visit.

When an individual test score of the ADAS-Cog-Exec composite is missing or not administered and the examiner indicated it is missing “for cognitive reasons”, the worst possible score is assigned for that individual test prior to constructing the ADAS-Cog-Exec score.

Potential confounders (baseline Walk Test time, age, education, 3MSE baseline score, and use of cholinesterase inhibitors) will be included in efficacy analyses as covariates if the following two conditions are satisfied: (1) imbalance at baseline ($p < 0.1$) and, (2) association between the covariate and the response ($p < 0.15$). Safety data will be analyzed using exact contingency table methods by intervention group assignment.

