- 12.2** Intervention effects on a supplemented ADAS-Cog-Exec that includes Letter Fluency (mean of F and L Fluency) will be examined in the mITT Population, the Pre-Pandemic Subset, and the Pandemic Subset using a similar approach described for Aim 1.
- 12.3** Intervention effects on the primary and key secondary outcomes will be examined in the Pandemic Subset using the approach described for Aim 1.
- 12.4** Subgroup analyses testing whether the following variables predict cognitive, vMRI, ASL MRI, and specimen biomarker response to the intervention in the mITT

Population and Pre-Pandemic Subset: sex, age, APOE genotype, baseline biomarker status (CSF: ab42/ab40, ab42/tau, ab42/p-tau; and blood: ab42/ab40).

12.5 In the Pandemic Subset, test whether pandemic-time-in-study altered intervention response on primary and key secondary outcomes. Pandemic-time-in-study coding is provided below.

- **Code 1:** At the time of study pause, participant had completed the Month 6 outcomes assessment (but not the Month 12 outcomes assessment)
- **Code 2:** At the time of study pause, participant was due for Month 6 or Month 12 outcomes assessment but did not complete until after the pause following a brief (6-8 weeks) ramp-up to prescribed intervention intensity.
- **Code 3:** At the time of study pause, participant had not yet completed an outcomes assessment.

13 Analyses of Executive Function and Episodic Memory Composites

Individual test scores included in each composite are listed below. Test scores are converted to z-scores and then averaged to create the composite score. Z-scores for longitudinal change are calculated by subtracting each participant's baseline score from the follow-up score (Month 6, Month 12) to obtain a change score, then dividing each change score by the baseline standard deviation for that measure. Composite scores are computed when 50% or more of the component test scores are available.

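### The plan asks whether baseline factors predict treatment response but names only subgroup analyses, and specifies no test that compares the effect between factor levels

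*Protocol*

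**What the plan says.** Protocol 1.2 sets Aim 7: "To examine whether gender, age, baseline AD biomarker profile, apolipoprotein epsilon 4 (ApoE4) genotypes, total activity, and sleep integrity predict treatment response". Protocol 5.4.2 adds baseline cognitive profile to the list. Its method is that "MMRM and sensitivity models as described above will be performed using subgroup analyses", followed by "Model fitting and covariate adjustment will be carried out as specified under Aim 1".

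The Aim 1 model is in Protocol 5.4.1: "The MMRM model will include terms for time, intervention, and baseline ADAS-Cog-Exec", then intervention-by-time and baseline-by-time interactions. Site, ApoE4 carrier status and sex enter as covariates. Age enters only if it passes the imbalance and association criteria. No term lets the intervention effect vary with a participant factor.

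The SAP makes the question exploratory in 5.3.6 ("To explore whether sex, age, baseline AD biomarker profile in CSF"...) and drops activity and sleep. SAP 12.4, under Sensitivity Analyses, gives the method: "Subgroup analyses testing whether the following variables predict cognitive, vMRI, ASL MRI, and specimen biomarker response". It lists sex, age, APOE genotype, three CSF ratios and one blood ratio, to be examined in the mITT population and the pre-pandemic subset. It names no model term, no between-subgroup test and no cut-points. The model it would inherit, in SAP 11.1, also lacks an intervention-by-factor term: "The MMRM model includes terms for time, intervention assignment, and baseline ADAS-Cog-Exec plus covariates that include site, ApoE4 carrier status, sex".

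**The concern.** Whether a factor predicts treatment response is a question about effect modification: does the difference between the arms itself differ between levels of the factor? A model fitted separately in men and in women gives two effect estimates and two p-values, but no estimate or test of the difference between them. Without a stated comparison, the obvious shortcut is to note that one subgroup is significant and the other is not. That happens often when the effect is the same in both, because each subgroup has much less power than the whole trial.

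The result at stake is a spurious finding such as benefit in ApoE4 non-carriers but not in carriers. Protocol 3.10 singles out ApoE4 carriage as a predictor of interest, so such a result would attract attention.

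A second gap is that age, the biomarker ratios and the actigraphy measures are continuous. If they are grouped at all, the cuts could be chosen after the data are seen.

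**Working it through.** **Inputs.** Difference 1.5, SD 4.1, two-sided 5%, 80% power, 20% attrition, 291 required and 300 targeted (Protocol 5.2); 296 enrolled (SAP 4); 1:1 allocation (Protocol 5.1). The documents give no subgroup shares and no power for Aim 7. The 50/50 and 30/70 splits are assumptions.

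**Plan's own figure.** n per arm = 2 × [4.1 × (1.960 + 0.842) / 1.5]² = 117.3, rounded up to 118. The total is 236, and 236 / 0.80 = 295 (293 without rounding). The stated 291 is within 3%, so the design values are confirmed. With 300 × 0.80 = 240 evaluable (120 per arm), overall power is 80.9%.

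**Power within subgroups, same true effect in both.** SE = 4.1 × √(2/n), with n per arm; power ≈ Φ(1.5/SE − 1.960).
- Equal halves, n = 60: SE = 0.749 and power is 51.8% in each half.
- 30/70 split, n = 36 and 84: SE = 0.966 and 0.633; power is 34.2% and 65.9%.

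**Chance that exactly one subgroup is significant** = p1(1 − p2) + p2(1 − p1).
- Equal halves: 2 × 0.518 × 0.482 = 49.9%.
- 30/70: 0.342 × 0.341 + 0.659 × 0.658 = 55.0%.

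Using 296 enrolled (296 × 0.80 = 236.8 evaluable) gives 50% and 55% again. With equal halves, the figure is 57% given a significant overall result. If exercise has no effect at all, it is 2 × 0.05 × 0.95 = 9.5%.

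**Interaction test on the same data.** SE of the difference in effects = 4.1 × √(2/n1 + 2/n2). The false-difference rate is 5% by construction (4.96% in simulation with equal halves).

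| Split | SE | Power for a 1.5-point difference in effects | Difference needed for 80% power |
|---|---|---|---|
| 50/50 | 1.059 | 29.4% | 2.97 |
| 30/70 | 1.155 | 25.5% | 3.24 |

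**Several factors.** With independent binary factors split equally and a uniform effect, simulation gives at least one significant/non-significant contrast in 79% of trials for 4 factors and 87% for 6. Unadjusted interaction tests give at least one false positive in 18% and 27%.

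**The case against.** The strongest reply is that the plan is silent rather than wrong. The term subgroup analysis is often used loosely and can include an interaction model. SAP 12.4 speaks of testing whether variables predict response, and names whole populations in which to do it. A strict within-stratum reading is also awkward, because the inherited covariates include sex and ApoE4, which are constant within their own strata. A reader might infer that the plan excludes an interaction term, or commits the team to comparing subgroup p-values. Neither document says so. A reader might also infer that age and the biomarker ratios will be cut into groups. SAP 12.4 refers to biomarker status, which hints at grouping, but no cut-point is given and nothing requires one.

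The 50–55% figure also rests on a decision rule that the plan does not contain, and on a true effect equal to the design value. The 5% for the alternative is per factor and accumulates over factors, outcomes and populations.

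All of this stands, and it limits the point to what is unspecified. It does not supply the missing test. Both documents write out intervention-by-time terms where they want them (Protocol 5.4.1, SAP 12.1), so an unstated intervention-by-factor term cannot be assumed.

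**Conclusion.** The concern holds as a gap in specification. The named method does not answer the question in Aim 7 and SAP 5.3.6, because no comparison of effects between factor levels is specified and the handling of continuous factors is left open.

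If subgroup p-values were contrasted, a uniform effect would look different between the two levels of a factor about 50–55% of the time, against 5% for an interaction test. This assumes a binary factor with a 50/50 to 30/70 split, ADAS-Cog design values standing in for ADAS-Cog-Exec, and a two-sample approximation to the MMRM. It measures the risk of a plausible misreading. It is not a forecast of what the team will report.

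The importance is modest. The aim is secondary in the protocol and exploratory in the SAP, and the primary test and the sample size are untouched.

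**What to change.** In SAP 12.4, and in Protocol 5.4.2 for Aim 7:

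- Fit the Aim 1 model in the full analysis population with the factor's main effect and an intervention-by-factor term, one factor at a time. The two-way term suits the SAP 11.1 contrast, which averages Months 6 and 12. Where the contrast is visit-specific, as in Protocol 5.4.1, add intervention-by-factor-by-time with its lower-order terms.
- Keep age, biomarker ratios and actigraphy measures continuous, or state cut-points in advance.
- Report each interaction estimate with its 95% confidence interval. Give subgroup estimates from the same model as description only.
- State that these analyses are exploratory, unadjusted across factors and outcomes, and low in power: about 25–29% for a 1.5-point difference in effects, with about 3.0–3.2 points (roughly twice the design effect) needed for 80%.

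The cost is wording only, with no new data, visits or participants. The drawback is that the interaction results will openly show how little the trial can say about who benefits more.

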## 5.5 Safety Analysis

Safety will be assessed by summarizing and analyzing AEs during the intervention period. Adverse events will be coded according to established Medical Dictionary for Regulatory Activities (MedDRA) terms and summarized by MedDRA System Organ Class and Preferred Term. Treatment-emergent adverse events (TEAE) will be defined as events that first occurred or worsened on or after randomization.

An overview of AEs, including the number and percentage of participants who died, suffered SAEs, discontinued due to AEs, and who suffered TEAEs, will be provided. A comparison between intervention arms will be performed. Summaries of AEs by within system organ class will be provided for: (1) pre-existing conditions, (2) TEAEs, and (3) SAEs. Discontinuations due to AEs will also be listed.

## 5.6 Termination of the Trial

No criteria for trial termination are specified. If safety or efficacy issues are identified during trial conduct, the Data and Safety Monitoring Board (DSMB) may decide to stop the study.

## 6.0 INTERVENTIONS AND IMPLEMENTATION

### 6.1 Overview

Participants will complete EXERT interventions at participating YMCAs located near the selected clinic sites across the U.S. The YMCA will provide 18-month memberships at no cost to participants. In the first 12 months, a study-certified YMCA Trainer will supervise all participants for the first 8 exercise sessions completed (weeks 1 and 2), and for 2 of 4 weekly sessions thereafter through Month 12. At this time, participants will transition to independent exercise and continue their assigned exercise programs for the final 6 months of the study without supervision. To encourage adherence and optimize cost efficiency, Trainers will provide supervision to small groups of participants (2-4 individuals) randomized to the same intervention whenever possible. Compliance will be evaluated using multiple mechanisms including HR monitoring, participant ratings of perceived exertion, entries in participants' Physical Activity Logs, Trainer assessment of effort, and weekly data review by the YMCA-Project Manager (Y-

PM) and the Intervention Oversight Team (includes the PDs, Wake Forest team of exercise trial specialists, and Y-USA). These mechanisms will provide multiple and regular opportunities to discuss participant progress, identify and resolve barriers, and encourage high levels of adherence to study protocols. The Intervention Oversight Team has the necessary expertise to successfully accomplish this objective in EXERT.

## **6.2 Collaboration with the YMCA**

EXERT has partnered with the national office of the YMCA (referred to as 'Y-USA') to provide exercise facilities and trained personnel to supervise participants as they complete their assigned intervention protocols. The YMCA Trainers maintain certifications to keep current with latest knowledge about fitness and its practice, and have experience supervising older adult exercise. This collaboration with the Y-USA will move the field forward in bridging the rift between academic research and health care delivery, thus providing additional important translational value to the study.

Study-certification of Trainers will involve completion of training regarding the study protocol, proper implementation of the interventions, data capture of adherence outcomes, and AE recording and reporting.

Intervention adherence data will be recorded by Trainers on Case Report Forms (CRFs) during supervised exercise sessions and will include type of exercise completed, HR during exercise, ratings of perceived exertion, and exercise duration and intensity. During supervised sessions, Trainers will also review participants' Physical Activity Logs to ensure they are properly completed and study goals are met, and complete an AE Checklist that will be faxed to the clinic for review and follow-up as per study protocol (see **Sections 14 and 15**). The Trainers and Y-PMs will provide regular updates as requested by the clinic, the Intervention Oversight Team, and the ADCS. All Y-PMs will attend a telephone conference twice per month, attended by Clinic YMCA Liaisons, the Intervention Oversight Team, and the ADCS to ensure efficient coordination and implementation of the intervention protocols. Trainers will also attend at least one telephone conference call per month with members of the Intervention Oversight Team.

